Participant diary ^t												X	X	X	
Phone calls ^u												X	X	X	X
Pharmacodynamics ^v															
Platelets ^w				X	X	X	X		X		X	X	X	X	X

	Screening/Transition period ^a	Loading dose		Weekly maintenance dosing								End of study			
				Weekly clinic visits					Visits every 2 weeks	Visits every 4 weeks	Visits every 8 weeks (minimum)				
Week		0				1-6					7-12 ^c	13-24 ^d	25+ ^e		
Day	D-56 to D-1	D1	D1	D1	D4 ^b	D8	D15	D22	D29	D36	D43	D44 - D85	D86 - D169	D170+	
Hour		0H	1H	4H											
Window					±1 d	±1 d	±1 d	±1 d	±1 d	±1 d	±1 d	±2 d	±3 d	±4 d	±14 d
BIVV020 dosing schedule															
Archival PD sample		PX00	PX01			PX02			PX03			PX04 ^y	PX05 ^r	PX06+	X
DNA sample for future research ^x		X													
Pharmacokinetics/ADA ^v															
BIVV020 plasma samples		P00	P01			P02	P03		P04		P05	P06 ^y	P07 ^r	P08+	X
Anti-BIVV020 antibodies		PD00							PD01			PD02 ^y	PD03 ^r	PD04+	X ^z

- ^a The Transition Period applies only to participants who were previously receiving sutimlimab, and is a period of at least 14 days between the last sutimlimab dose and the first dose of BIVV020. This period is included as part of the Screening Period.
- ^b The Day 4 visit may be performed at the participant's home using a home nursing service.
- ^c Visits will occur at Weeks 8, 10, and 12.
- ^d Visits will occur at Weeks 16, 20, and 24.
- ^e Visits will occur at Weeks 32, 40, 48, etc, with phone calls occurring approximately 4 weeks after each visit. Participants will continue to receive BIVV020 until the last participant enrolled has completed 52 weeks of treatment. For the last participant enrolled, a visit should occur at Week 52. Visits should occur around the time a participant is transitioning off BIVV020, even if this visit is less than 8 weeks from the prior visit. The maximum duration of treatment for an individual participant is 104 weeks.
- ^f Inclusion and exclusion criteria should be reviewed on Day 1 prior to enrollment.
- ^g Participants should have documented vaccination against encapsulated bacterial pathogens (*Neisseria meningitidis*, including serogroup B meningococcus [where available]), *Haemophilus influenzae*, and *Streptococcus pneumoniae*) within 5 years prior to enrollment. The participant should receive the vaccine series as early as possible. See [Section 8.2.6](#) for additional details.

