9.3.2 Primary endpoint

The primary endpoint is described in [Section 3](#).

The number and proportion of participants meeting the responder criteria will be presented; the 95% confidence interval of the proportion of responders will be estimated using Clopper-Pearson method. Missing data will not be imputed in the statistical analysis. If a patient discontinues study treatment prior to Week 3, the patient will be considered as a non-responder. If a patient discontinues the study treatment after Week 3 and prior to Week 24, his or her responder status will be assessed using the available data between Week 3 and Week 24.

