10.8 APPENDIX 8: COUNTRY-SPECIFIC REQUIREMENTS

Not applicable.

10.9 APPENDIX 9: CONTINGENCY MEASURES FOR A REGIONAL OR NATIONAL EMERGENCY THAT IS DECLARED BY A GOVERNMENTAL AGENCY

The following contingencies may be implemented for the duration of the emergency (after Sponsor agreement is obtained).

Study intervention

If a participant has to stop BIVV020 due to a regional or national emergency (eg, COVID-19), re-initiation of the study intervention can only occur once the Investigator has determined, according to his/her best judgement, that 1) BIVV020 did not contribute to the occurrence of the concerned adverse event and 2) the selection criteria for the study are still met (refer to [Section 5](#)). Re-initiation of the study intervention will be done under close and appropriate clinical/and or laboratory monitoring and in consultation with the Sponsor.

Study assessments and procedures

During the emergency, if the site will be unable to adequately follow protocol mandated procedures, alternative treatment outside the clinical trial should be proposed, and screening/enrollment/administration of study intervention may be temporarily delayed.

Attempts should be made to perform all assessments in accordance with the approved protocol to the extent possible. In case this is not possible due to a temporary disruption caused by an emergency, focus should be given to assessments necessary to ensure the safety of participants and those important to preserving the main scientific value of the study.

Procedures to be considered in the event of a regional or national emergency declared by a governmental agency:

- If onsite visits are not possible, remote visits (eg, with home nurses, home health vendor, etc) may be planned for the collection of possible safety and/or efficacy data.
- If onsite visits are not possible, visit windows may be extended for assessment of safety and/or efficacy data that cannot be obtained remotely.
- Use of local clinic or laboratory locations may be allowed when central labs cannot be performed due to a government declared national emergency.

Statistical analyses

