The impact of the regional or national emergency declared by a governmental agency on study conduct will be summarized (eg, study discontinuation or discontinuation/delay/omission of the intervention due to the emergency). Any additional analyses and methods required to evaluate the impact on efficacy (eg, missing data due to the emergency) and safety will be detailed in the SAP.

Informed consent

For a regional or national emergency declared by a governmental agency, contingency procedures may be implemented for the duration of the emergency. The participant or their legally authorized representative should be verbally informed prior to initiating any changes that are to be implemented for the duration of the emergency (eg, study visit delays/treatment extension, use of local labs).

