### Analysis windows for time points

The following analysis windows will decide how the scheduled and/or unscheduled visits will be used in the by-visit analyses of efficacy, safety, PK and ADA variables.

A measurement (scheduled or unscheduled) will be used if it is available and measurement date is within the analysis window.

After applying these time windows, if multiple assessments are associated to the same time point, the closest from the targeted study day will be used. If the difference is a tie, the value after the targeted study day will be used. If multiple valid values exist within a same day, then the first value of the day will be selected.

If there is no measurement for a given parameter in an analysis window, data will be considered missing for the corresponding visit.

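### SAP Table 6 targets Week 10 at Day 80 and Week 32 at Day 171, so on-time platelet counts at both visits fall in no window and become missing

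*SAP*

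**What the plan says.** SAP 5.4 (Analysis windows for time points) sets out "how the scheduled and/or unscheduled visits will be used in the by-visit analyses of efficacy, safety, PK and ADA variables". Its condition is: "A measurement (scheduled or unscheduled) will be used if it is available and measurement date is within the analysis window". If nothing qualifies: "If there is no measurement for a given parameter in an analysis window, data will be considered missing for the corresponding visit". Table 6 then prints a target day and tolerance for each visit, including Week 10 at 80 (±2), Week 24 at 169 (±4) and Week 32 at 171 (±4). The Study Day paragraph of the same section makes the first dose Day 1.

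The protocol's Schedule of Activities (1.3) states for the two-weekly phase: "Visits will occur at Weeks 8, 10, and 12". Visits follow at Weeks 16, 20 and 24, and then at Weeks 32, 40, 48 and so on. Permitted visit windows are ±1 day for the weekly visits, ±2 days for Weeks 7–12, ±3 days for Weeks 13–24 and ±4 days from Week 25.

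The primary endpoint (Protocol 3, SAP 4.3) asks whether the platelet threshold is met at half or more of the scheduled visits from Week 3 to Week 24. Protocol 9.3.2 adds: "Missing data will not be imputed in the statistical analysis".

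On emergencies, Protocol Appendix 9 (10.9) says: "If onsite visits are not possible, visit windows may be extended for assessment of safety and/or efficacy data that cannot be obtained remotely". It leaves the methods for evaluating the impact on efficacy to the other document: "eg, missing data due to the emergency) and safety will be detailed in the SAP". The SAP's only provision is a summary of Covid-19-affected participants, under protocol deviations in 4.2.

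**The concern.** A window table decides which value represents which visit. If a target day is wrong by more than the tolerance, a participant who attends exactly on schedule has no usable value at that visit, and the loss is the same for everyone.

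Week 10 sits inside the primary assessment period. The endpoint is a fraction of a small number of visits with a cut at 50%, so one systematically missing visit can decide a borderline participant. With about 12 participants, one changed status is visible in the reported rate.

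Week 32 lies outside the primary period, but its misplaced window reaches back over Week 24. Week 24 is both the last primary visit and a time point for the secondary response rate.

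**Working it through.** **Inputs.** Day 1 = first dose (SAP 5.4). Visit weeks and permitted windows come from Protocol 1.3. Analysis targets and tolerances come from SAP Table 6.

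**Step 1: reproduce the targets.** Nominal day = 7 × week + 1.

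| Visit | Nominal day | Protocol window | Table 6 target | Table 6 window |
|---|---|---|---|---|
| D22, D29, D36, D43 | 22, 29, 36, 43 | ±1 | same | ±1 |
| Week 8 | 57 | 55–59 | 57 | 55–59 |
| **Week 10** | **71** | **69–73** | **80** | **78–82** |
| Week 12 | 85 | 83–87 | 85 | 83–87 |
| Week 16 | 113 | 110–116 | 113 | 110–116 |
| Week 20 | 141 | 138–144 | 141 | 138–144 |
| Week 24 | 169 | 166–172 | 169 | 165–173 |
| **Week 32** | **225** | **221–229** | **171** | **167–175** |
| Week 40 | 281 | 277–285 | 281 | 277–285 |

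Every target reproduces except Week 10 (80 against 7 × 10 + 1 = 71) and Week 32 (171 against 7 × 32 + 1 = 225). SAP 5.2 reports no changes to the protocol-planned analyses, so nothing suggests that either was moved on purpose.

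**Step 2: Week 10.** Week 8 ends on Day 59 and the printed Week 10 window starts on Day 78. Of the five permitted days, 69 to 73, none lies in any window. The printed slot could be filled only by a count taken 78 − 71 = 7 to 82 − 71 = 11 days after the nominal visit.

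**Step 3: Week 32.** None of the nine permitted days, 221 to 229, lies in a printed window. The printed window, 167–175, shares Days 167–173 with Week 24. Six of the seven days on which the protocol allows the Week 24 visit (167–172 out of 166–172) therefore belong to two visits. The tie rules in SAP 5.4 choose among several values for one visit; they do not place one value that fits two visits.

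**Step 4: share of the primary endpoint.** If every on-site visit carries a platelet count, as SAP 1.1 says, there are 10 visits: D22, D29, D36, D43 and Weeks 8, 10, 12, 16, 20 and 24. The Schedule of Activities, as extracted, seems to leave D22 and D36 blank for platelets, which would make 8. Week 10 is thus 1/10 to 1/8 of the visits.

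**Step 5: effect on a borderline participant.** The SAP does not say whether a missing visit stays in the denominator, so both cases are shown.

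| True result | Week 10 count lost | Fixed denominator | Available visits |
|---|---|---|---|
| 5/10 | qualifying | 4/10 = 40% | 4/9 = 44% |
| 4/8 | qualifying | 3/8 = 38% | 3/7 = 43% |
| 4/10 | non-qualifying | 4/10 = 40% | 4/9 = 44% |
| 3/8 | non-qualifying | 3/8 = 38% | 3/7 = 43% |

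Losing a qualifying count turns a responder into a non-responder under either denominator. If no other visit is missing, losing a non-qualifying Week 10 count does not create a responder. It can do so on available visits if another non-qualifying count is already missing: 4/9 = 44% becomes 4/8 = 50%.

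**Step 6: effect on the rate.** One changed status is 1/12 = 8.3 percentage points. For example, 6/12 (Clopper-Pearson 95% CI 21–79%) becomes 5/12 (15–72%). In a subgroup assumed to have 6 participants, the change is 1/6 = 16.7 points.

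**The case against.** **SAP 4.3 does not cite Table 6.** The windows are introduced for by-visit analyses, and a programmer could count primary visits by their nominal label. This stands: loss from the primary endpoint is the natural reading, not an express statement. But Table 6 is the SAP's only rule that ties a platelet count to a scheduled visit, and the loss from the by-visit efficacy analyses is express.

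**The two cells are evident slips that would be noticed.** Probably so, since every other listed target fits one formula. That makes the repair easy, but it does not make the printed rule usable.

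**A stronger reading is tempting.** Because the windows are narrow with gaps between them, a reader might infer that counts a day or two off schedule are generally thrown away. The documents do not support this. Apart from the two wrong targets, the listed windows equal the protocol's visit windows, and Week 24 is wider (±4 against ±3). A one-day slip never loses a count through window width, and a two-day slip loses one only at the ±1-day weekly visits, where it is already outside the protocol's window. Days outside any window mostly hold no planned count, so calendar coverage does not measure lost data. Whether to widen the windows until they meet is a trade-off between keeping counts and keeping visit timing. The present choice is defensible in a descriptive study.

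**The emergency point is limited.** Appendix 9 also offers remote visits and local laboratories, and extends windows only for data that cannot be obtained remotely. Few platelet counts may be affected. Still, the SAP says nothing about those that are.

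**Conclusion.** Table 6 is wrong as printed at Week 10 and Week 32. Every on-time Week 10 platelet count is set to missing for every participant in the by-visit efficacy analyses and, on the natural reading, in the primary endpoint, where it is one of 8 to 10 visits. On-time Week 32 values are lost as well, and most permitted Week 24 dates fall under two visits. The practical effect falls on borderline participants: one changed status moves the rate 8.3 points at n = 12. The documents give no basis for predicting how many participants will be borderline.

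This rests on two assumptions: that Table 6 governs the responder count, and that the visit total is 8 or 10. The target-day errors themselves need neither.

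A secondary gap is that the SAP has no rule for counts collected under the protocol's emergency extension, although the protocol promised such methods there. The conclusion does not extend to the general width of the windows.

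**What to change.** 1. In Table 6, change the Week 10 target to Day 71 (±2) and the Week 32 target to Day 225 (±4). This restores on-time values at both visits and removes the overlap with Week 24.
2. In SAP 4.3, state that Table 6 assigns platelet counts to scheduled visits for the primary endpoint. The same sentence can say whether a visit without a count stays in the denominator.
3. In SAP 5.4, state that a scheduled-visit count taken under an emergency window extension is kept for its nominal visit rather than set to missing.

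The cost is two table cells and two or three sentences, with no change to data collection. The same windows serve the by-visit safety, PK and ADA outputs, so their programming specifications need the same correction. Any by-visit output already produced from the printed table should be rerun. The changes should be documented before further analysis, because the study is open-label and the assignment should not be decided count by count.

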### **Unscheduled visits**

Unscheduled visit measurements of laboratory data, vital signs, ECG and ADA will be used for computation of baseline, the last on-treatment value, analysis according to PCSAs, and the shift summaries for safety. They will also be included in the by-visit summaries if they are re-allocated to scheduled visits.

### **5.5 APPENDIX 5 WHO BLEEDING SCALE**

Coded Grade of Bleeding	Decoded Grade of Bleeding
1	Petechiae
2	Mild blood loss
3	Gross blood loss
4	Debilitating blood loss

## 5.6 APPENDIX 6 CRITERIA FOR POTENTIALLY CLINICALLY SIGNIFICANT ABNORMALITIES

### CRITERIA for POTENTIALLY CLINICALLY SIGNIFICANT ABNORMALITIES

Parameter	PCSA	Comments
Clinical Chemistry		
ALT	By distribution analysis : >3 ULN >5 ULN >10 ULN >20 ULN	Enzymes activities must be expressed in ULN, not in IU/L. Concept paper on DILI – FDA draft Guidance Oct 2007. Internal DILI WG Oct 2008. Categories are cumulative. First row is mandatory. Rows following one mentioning zero can be deleted.
AST	By distribution analysis : >3 ULN >5 ULN >10 ULN >20 ULN	Enzymes activities must be expressed in ULN, not in IU/L. Concept paper on DILI – FDA draft Guidance Oct 2007. Internal DILI WG Oct 2008. Categories are cumulative. First row is mandatory. Rows following one mentioning zero can be deleted.
Alkaline Phosphatase	>1.5 ULN	Enzymes activities must be expressed in ULN, not in IU/L. Concept paper on DILI – FDA draft Guidance Oct 2007. Internal DILI WG Oct 2008.
Total Bilirubin	>1.5 ULN >2 ULN	Must be expressed in ULN, not in $\mu\text{mol/L}$ or mg/L. Categories are cumulative. Concept paper on DILI – FDA draft Guidance Oct 2007. Internal DILI WG Oct 2008.
Conjugated Bilirubin	>35% Total Bilirubin and TBILI>1.5 ULN	Conjugated bilirubin dosed on a case-by-case basis.
ALT and Total Bilirubin	ALT>3 ULN and TBILI>2 ULN	Concept paper on DILI – FDA draft Guidance Oct 2007. Internal DILI WG Oct 2008. To be counted within a same treatment phase, whatever the interval between measurement.
CPK	>3 ULN >10 ULN	FDA Feb 2005. Am J Cardiol April 2006. Categories are cumulative. First row is mandatory. Rows following one mentioning zero can be deleted.

**CRITERIA for POTENTIALLY CLINICALLY SIGNIFICANT ABNORMALITIES**

Parameter	PCSA	Comments
CLcr (mL/min) (Estimated creatinine clearance based on the Cokcroft-Gault equation)	<15 (end stage renal disease) ≥15 - <30 (severe decrease in GFR) ≥30 - < 60 (moderate decrease in GFR) ≥60 - <90 (mild decrease in GFR) ≥ 90 (normal GFR)	FDA draft Guidance 2010 Pharmacokinetics in patients with impaired renal function-study design, data analysis, and impact on dosing and labeling
eGFR (mL/min/1.73m  ) (Estimate of GFR based on an MDRD equation)	<15 (end stage renal disease) ≥15 - <30 (severe decrease in GFR) ≥30 - < 60 (moderate decrease in GFR) ≥60 - <90 (mild decrease in GFR) ≥ 90 (normal GFR)	FDA draft Guidance 2010 Pharmacokinetics in patients with impaired renal function-study design, data analysis, and impact on dosing and labeling
Creatinine	≥150 µmol/L (Adults) ≥30% change from baseline ≥100% change from baseline	Benichou C., 1994.
Uric Acid		Harrison- Principles of internal Medicine 17 th Ed., 2008.
Hyperuricemia	>408 µmol/L	
Hypouricemia	<120 µmol/L	
Blood Urea Nitrogen	≥17 mmol/L	
Chloride	<80 mmol/L >115 mmol/L	
Sodium	≤129 mmol/L ≥160 mmol/L	
Potassium	<3 mmol/L ≥5.5 mmol/L	FDA Feb 2005.
Total Cholesterol	≥7.74 mmol/L	Threshold for therapeutic intervention.
Triglycerides	≥4.6 mmol/L	Threshold for therapeutic intervention.
Lipasemia	≥3 ULN	
Amylasemia	≥3 ULN	
Glucose		
Hypoglycaemia	≤3.9 mmol/L and <LLN	ADA May 2005.
Hyperglycaemia	≥11.1 mmol/L (unfasted); ≥7 mmol/L (fasted)	ADA Jan 2008.
HbA1c	>8%	
Albumin	≤25 g/L	
CRP	>2 ULN or >10 mg/L (if ULN not provided)	FDA Sept 2005.

**CRITERIA for POTENTIALLY CLINICALLY SIGNIFICANT ABNORMALITIES**

Parameter	PCSA	Comments
Hematology		
WBC	<3.0 Giga/L (Non-Black); <2.0 Giga/L (Black) ≥16.0 Giga/L	Increase in WBC: not relevant. To be interpreted only if no differential count available.
Lymphocytes	>4.0 Giga/L	
Neutrophils	<1.5 Giga/L (Non-Black); <1.0 Giga/L (Black)	International Consensus meeting on drug-induced blood cytopenias, 1991. FDA criteria.
Monocytes	>0.7 Giga/L	
Basophils	>0.1 Giga/L	
Eosinophils	>0.5 Giga/L or >ULN (if $ULN \geq 0.5$ Giga/L)	Harrison- Principles of internal Medicine 17 th Ed., 2008.
Hemoglobin	≤115 g/L (Male); ≤95 g/L (Female) ≥185 g/L (Male); ≥165 g/L (Female)  Decrease from Baseline ≥20 g/L	Criteria based upon decrease from baseline are more relevant than based on absolute value. Other categories for decrease from baseline can be used (≥30 g/L, ≥40 g/L, ≥50 g/L).
Hematocrit	≤0.37 v/v (Male) ; ≤0.32 v/v (Female) ≥0.55 v/v (Male) ; ≥0.5 v/v (Female)	
RBC	≥6 Tera/L	Unless specifically required for particular drug development, the analysis is redundant with that of Hb. Otherwise, consider FDA criteria.
Platelets	<100 Giga/L ≥700 Giga/L	International Consensus meeting on drug-induced blood cytopenias, 1991.
Urinalysis		
pH	≤4.6 ≥8	
Vital signs		
HR	≤50 bpm and decrease from baseline ≥20 bpm ≥120 bpm and increase from baseline ≥20 bpm	To be applied for all positions (including missing) except STANDING.
SBP	≤95 mmHg and decrease from baseline ≥20 mmHg ≥160 mmHg and increase from baseline ≥20 mmHg	To be applied for all positions (including missing) except STANDING.
DBP	≤45 mmHg and decrease from baseline ≥10 mmHg ≥110 mmHg and increase from baseline ≥10 mmHg	To be applied for all positions (including missing) except STANDING.
Orthostatic Hypotension		
Orthostatic SDB	≤-20 mmHg	
Orthostatic DBP	≤-10 mmHg	

**CRITERIA for POTENTIALLY CLINICALLY SIGNIFICANT ABNORMALITIES**

Parameter	PCSA	Comments
Weight	≥5% increase from baseline ≥5% decrease from baseline	FDA Feb 2007.
ECG		Ref.: ICH E14 guidance (2005) and E14 Q&A (2012), and Cardiac Safety Research Consortium White Paper on PR and QRS (Nada et al. Am Heart J. 2013; 165(4) : 489-500)
HR	<50 bpm <50 bpm and decrease from baseline ≥20 bpm <40 bpm <40 bpm and decrease from baseline ≥20 bpm <30 bpm <30 bpm and decrease from baseline ≥20 bpm  >90 bpm >90 bpm and increase from baseline ≥20bpm >100 bpm >100 bpm and increase from baseline ≥20bpm >120 bpm >120 bpm and increase from baseline ≥20 bpm	Categories are cumulative
PR	>200 ms >200 ms and increase from baseline ≥25% > 220 ms >220 ms and increase from baseline ≥25% > 240 ms > 240 ms and increase from baseline ≥25%	Categories are cumulative
QRS	>110 ms >110 msec and increase from baseline ≥25% >120 ms >120 ms and increase from baseline ≥25%	Categories are cumulative
QT	>500 ms	
QTc	Absolute values (ms) >450 ms >480 ms >500 ms Increase from baseline Increase from baseline ]30-60] ms Increase from baseline >60 ms	To be applied to any kind of QT correction formula. Absolute values categories are cumulative  QTc >480 ms and ΔQTc >60 ms are the 2 PCSA categories to be identified in individual subjects/patients listings.

Signature Page for VV-CLIN-0608226 v1.0  
pdy16894-16-1-9-sap

Approve & eSign

[REDACTED]  
Clinical

Approve & eSign

[REDACTED]  
Clinical
